10.3.3.2 Secondary Analyses

Analysis of key secondary endpoint of proportion of all-cause allograft failure at the end of 48 months after enrollment

The primary comparison for the proportion of subjects with all-cause allograft failure at the end of 48 months after enrollment will be based on a logistic regression model. The randomized treatment groups, C1-INH and placebo, will be compared based on the logistic model.

The same logistic model as described for the primary endpoint will also be used for this analysis.

Analysis of components of all-cause allograft failure after enrollment into TP1 through the Responder Follow-up Period (ie, within 48 months after enrollment) will be summarized for the randomized treatment groups and also the non-responder subjects who were not randomized in TP2. The summary will be based on the proportion of subjects with:

- Any event (ie, all-cause allograft failure or death by any cause).
- All-cause allograft failure (defined by allograft nephrectomy, or institution of permanent dialysis, or return to the transplant waitlist for renal transplant);
- Surviving allografts
- Death by any cause

Proportion of subjects with all cause allograft failure will be also summarized by treatment groups at 1 year, 2 years, and 3 years since enrollment.

Analysis of key secondary endpoint of time to all-cause allograft failure through 48 months after enrollment

Treatment group differences will be analyzed with a Cox proportional hazards regression model with randomization strata as covariates. This model will be used to estimate the C1-INH /placebo hazard ratio and two-sided 95% confidence interval. Kaplan-Meier plots of time to failure through the Responder Follow-up Period will be produced.

Subgroup analysis of loss-of-response at the End-of-TP2

Details of subgroup analyses will be provided in the SAP.

The following subgroups, and possibly others to be described in the SAP, will be summarized by treatment group with respect to the proportion of loss-of-response:

- Geographic region: USA, non-USA.
- DSA by randomization strata: sensitized, de novo.
- DSA by classification: HLA class I, HLA class II, both HLA class I and II.
- AMR severity: severe, non-severe (all other severities).
- Type of donor: deceased, living.
- Recipient race: Black, non-Black.
- Recipient sex: male, female.
- Recipient age: < 65 years, \geq 65 years.

Subgroup analysis of all-cause allograft failure at the end of 48 months after enrollment

Subject Proportions by treatment group for components of all-cause allograft failure will be presented for similar subgroups as described above

Analysis of responders at the End-of-TP1

The proportion of responders at the End-of-TP1 will be presented together with an exact 95% confidence interval. To calculate this proportion, the denominator will include all subjects in the Enrolled analysis set, and the numerator will include all subjects meeting the definition of response (Section 8.1.3.2).

The eGFRs during TP1 (ie, with open-label C1-INH) will be summarized by scheduled visit using descriptive statistics, as will the absolute and percent changes from baseline. The descriptive statistics will use available data from the Enrolled analysis set (ie, missing data will be not imputed).

CCI

CCI

CCI

New or worsening chronic active AMR

The proportion of subjects with new or worsening chronic active AMR during TP2, as defined by the Banff 2015 Criteria [Loupy et al, 2017], will be analyzed using the logistic model as described for the primary efficacy endpoint and also with this model stratified by the randomization strata, for the ITT analysis set.

Splenectomy

The proportion of subjects with splenectomy during TP1 will be summarized. Descriptive statistics of time from first dose of C1-INH will be presented. Splenectomy during TP1 will be summarized for the Enrolled analysis set.

The proportions of subjects with splenectomy during TP2 will be summarized by treatment group. Descriptive statistics for time from first dose of C1-INH, and time from last dose of C1-INH will be presented. Splenectomy during TP2 will be summarized for the ITT analysis set.

C1-esterase inhibitor functional activity

C1-esterase inhibitor functional activity at the designated time points will be summarized using descriptive statistics.

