3.3 Scientific Rationale

3.3.1 Study Design Rationale

Antibodies directed against a transplanted donor organ (ie, DSA) activate the complement system, resulting in direct and indirect damage to the allograft. Complement-mediated damage as a result of AMR is recognized as an important cause of poor long-term allograft and patient survival.

Although no therapies have been approved for the treatment of AMR, the current standard of care most commonly consists of intravenously administered immunoglobulin (IVIg) with or without plasmapheresis and/or rituximab. These regimens can result in acceptable short-term allograft survival for kidney transplant patients with AMR. However, approximately 25% of patients with AMR are refractory to standard therapies, and eGFR continues to decline despite first-line treatment [Viglietti et al, 2016a]. Approximately 20% of patients with active AMR have simultaneous chronic active AMR [Viglietti et al, 2018, Aubert et al, 2019], which is generally not amenable to treatment and whose natural history is progressive loss of function [Loupy and Lefaucheur, 2018]. In addition, approximately 50% of patients with active AMR have simultaneous chronic active T-cell mediated rejection [Viglietti et al, 2018]. Not surprisingly, therefore, up to 90% of grafts in these patients fail within 4 years of the diagnosis of refractory AMR. The addition of complement inhibition therapy to standard of care has been reported in the literature to successfully treat acute AMR that is unresponsive to treatment with a standard of care regimen [Viglietti et al, 2016a].

In that study, all subjects showed an improvement in eGFR as the key indicator of clinical response to complement inhibitor therapy. Estimated GFR is a functionally important, therapeutically relevant, and clinically accepted surrogate marker of allograft survival. In a recent AMR workshop sponsored by the FDA, GFR was considered as a potentially acceptable surrogate marker for pivotal clinical trial(s) of an interventional therapy to treat acute AMR [Archeacon et al, 2011]. Studies in transplantation have shown that eGFR by the

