10.1.2 Power for Allograft Survival

Allograft survival status (or all-cause allograft failure) at the end of 48 months after enrollment represents clinical confirmation of the effect on the allograft of improving eGFR.

The primary comparison of the proportion of subjects with allograft survival will be between the subjects randomized to placebo or C1-INH. It is anticipated that very few subjects will be lost to follow-up as standard of care mandates close follow up by the transplanting center. This endpoint will be analyzed after all subjects have been followed for 4 years after enrollment.

The power for hypothesis testing of this endpoint was estimated using the power procedure in SAS STAT under the following assumptions:

- The proportions of subjects with allografts surviving at 4 years after enrollment will be 0.25 with the placebo cohort and 0.75 in the C1-INH cohort.
- Alpha = 0.05 (two-sided test).

- Logistic regression model with treatment effect will be used for the primary efficacy analysis. Wald test statistic for treatment effect from Logistic regression has approximately same distribution as chi-square [[Fleiss et al, 2003](#)]. Therefore, the sample size calculation based on chi-square test is used to ensure similar power for hypothesis testing.
- Approximately 30 subjects in each randomized treatment groups.

There is greater than 90% power to detect the specified target difference between C1-INH and placebo groups based on sample size of 60 (approximately 30 in the C1-INH cohort and approximately 30 in the placebo cohort).

The 4-year graft survival for placebo of 25% is based on data presented at the American Transplant Congress in Boston [[Viglietti et al, 2016b](#)]. This study involved follow-up of kidney transplant recipients with biopsy-proven active AMR diagnosed between 2007 and 2013. Among the subjects who have not responded to standard of care, the 4-year graft survival ranged from approximately 10% to 40% for subjects with high and intermediate risk scores, respectively. The 4-year graft survival for C1-INH of 75% represents what would be expected for subjects who are successfully treated.

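### The planned 48-month graft-failure models leave out End-of-TP1 eGFR, a pre-randomization value already held for every randomized subject; the power lost is negligible at the planned effect but can reach several points if the effect is smaller

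*Protocol*

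**What the plan says.** Protocol Section 10.3.3.1 defines the primary logistic model with an intercept and a treatment indicator, and states that the stratification factors are left out. For the key secondary endpoint, the proportion with all-cause graft failure at 48 months, Section 10.3.3.2 says: "The same logistic model as described for the primary endpoint will also be used for this analysis". For time to failure it says: "Treatment group differences will be analyzed with a Cox proportional hazards regression model with randomization strata as covariates". The strata are DSA origin (sensitized or de novo) and AMR severity (oliguria or anuria in the current episode, or not). eGFR is in neither model. Section 10.3.3.1 allows further key covariates, but only in the sensitivity analysis of loss-of-response at the End-of-TP2.

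End-of-TP1 eGFR is the mean of the Week 11 and Week 12 values. Responder status is settled from it at Week 13, when responders are randomized (Protocol Sections 8.1.3.2 and 10.3.1), so it precedes randomization and exists for every subject correctly classified as a responder. On eGFR in general, Section 3.3.1 says: "Estimated GFR is a functionally important, therapeutically relevant, and clinically accepted surrogate marker of allograft survival".

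Section 10.1.2 gives the power statement for 48-month graft survival: "There is greater than 90% power to detect the specified target difference between C1-INH and placebo groups".

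**The concern.** A baseline variable that predicts the outcome normally belongs in the model of a small randomized trial. On the protocol's own account, declining function is the route to graft loss: Section 1.1 describes GFR falling until dialysis or re-transplantation is needed, and permanent dialysis is one of the events that define graft failure.

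The only reason given for a model without covariates is that efficacy is not expected to differ between strata. That is an argument about effect modification and does not address prognosis. Randomization is not stratified on function at Week 13, and the responder rule (at least 20 mL/min/1.73 m² and at least 90% of the subject's own baseline) sets a floor without a ceiling.

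What is at stake is power for the one secondary endpoint in the gatekeeping hierarchy of Section 10.3. An adjusted analysis would also account for any chance difference in starting function between two arms of about 30.

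**Working it through.** **Inputs from Protocol Section 10.1.2.** Graft survival "will be 0.25 with the placebo cohort and 0.75 in the C1-INH cohort", that is, failure 0.75 versus 0.25; two-sided alpha 0.05; about 30 per arm. For the source of the placebo rate: "the 4-year graft survival ranged from approximately 10% to 40% for subjects with high and intermediate risk scores, respectively".

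**Inputs assumed.** The documents do not say how strongly End-of-TP1 eGFR predicts 48-month failure. The range used is an odds ratio for failure per SD of 1 to 4 (logistic) and a hazard ratio per SD of 1 to 3 (Cox).

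**Step 1: the stated power.** For two proportions with n = 30 per arm:

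- Null SE = √(2 × 0.5 × 0.5 / 30) = 0.1291.
- Alternative SE = √((0.75 × 0.25 + 0.25 × 0.75) / 30) = 0.1118.
- z = (0.50 − 1.96 × 0.1291) / 0.1118 = 2.21, so power = 98.6%.

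The likelihood-ratio approximation gives 97.7%, and exact enumeration of the unadjusted Wald test gives 98.4%. The claim of more than 90% is reproduced.

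**Step 2: a smaller effect anchored in the protocol.** Take placebo survival at the 40% end of the source and keep C1-INH survival at 75%, so failure is 0.60 versus 0.25:

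- Mean failure = 0.425; null SE = √(2 × 0.425 × 0.575 / 30) = 0.1276.
- Alternative SE = √((0.60 × 0.40 + 0.25 × 0.75) / 30) = 0.1194.
- z = (0.35 − 1.96 × 0.1276) / 0.1194 = 0.84, so power is about 80%.

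**Step 3: logistic model with and without eGFR.** Simulation with 30 per arm and 10,000 trials per row. One standard normal covariate stands for log End-of-TP1 eGFR, marginal failure rates are held fixed, and the Wald test is used. Gains come from unrounded values.

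| Failure, placebo vs C1-INH | Odds ratio per SD | Without eGFR | With eGFR | Gain (points) |
|---|---|---|---|---|
| 0.75 vs 0.25 (planned) | 1 | 98.4% | 98.3% | −0.1 |
| | 1.5 | 98.4% | 98.6% | +0.1 |
| | 2 | 98.2% | 98.6% | +0.4 |
| | 3 | 98.6% | 99.4% | +0.8 |
| | 4 | 98.5% | 99.6% | +1.2 |
| 0.60 vs 0.25 | 1 | 80.0% | 79.6% | −0.4 |
| | 1.5 | 79.9% | 80.5% | +0.6 |
| | 2 | 79.4% | 82.2% | +2.9 |
| | 3 | 80.7% | 86.6% | +5.9 |
| | 4 | 79.7% | 88.4% | +8.7 |

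The mirror-image case, failure 0.75 versus 0.40, gives 83.3%, 86.1% and 88.9% with eGFR at odds ratios of 2, 3 and 4. Over all scenarios run, the largest cost when eGFR carries no information is 0.8 points (failure 0.60 versus 0.30). With no treatment effect, the adjusted test rejects in 4.2% to 5.1% of trials.

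**Step 4: Cox model.** 4,000 trials per case, exponential times, censoring only at 48 months, two uninformative strata in both models.

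- Planned 0.75 versus 0.25: adding eGFR gains 0.7 to 0.9 points at hazard ratios per SD of 1.5 to 3.
- Failure 0.75 versus 0.40 (the 0.40 is an assumption, not a figure in the documents): 81.2% to 85.0%, 83.4% to 91.9% and 84.7% to 97.7% at hazard ratios of 1.5, 2 and 3, gains of 3.7, 8.5 and 13.0 points.
- Uninformative eGFR: a cost of at most 0.3 points.
- No treatment effect: rejection in 5.3% to 6.1% of trials with eGFR and 4.6% to 6.4% without, so this small-sample Wald test runs slightly high in either form.

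**Step 5: chance imbalance.** The SD of the between-arm difference in a standardized covariate is √(2/30) = 0.26. A difference beyond 0.5 SD therefore arises in about 5% of trials. At an odds ratio of 2 to 3 per SD it shifts the failure odds by √2 = 1.4 to √3 = 1.7 fold.

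**The case against.** The unadjusted randomized comparison is valid. Chance imbalance is already covered by its type I error, so it is sampling variation and not bias. The Cox model is partly adjusted, through an AMR-severity stratum related to graft function. At the planned effect the gain is about a point or less. All of this stands, and it limits the point to efficiency.

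Some stronger conclusions that a reader might draw are not supported:

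- That the stated power of more than 90% is unsafe. It reproduces at about 98%.
- That eGFR is the dominant source of variation in 48-month failure. No passage quantifies its prognostic strength or its spread among responders.
- That the protocol names End-of-TP1 eGFR as the surrogate. The sentence in Section 3.3.1 concerns eGFR in general.
- That randomized subjects may have any eGFR above 20. They must also hold at least 90% of baseline, and the responder filter may narrow the spread.

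A technical objection is that the exact-logistic fallback in Section 10.3.3.1 works poorly when conditioned on a continuous covariate. That is correct, but separation occurred in at most 0.1% of simulated trials, and the fallback can be specified without eGFR.

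**Conclusion.** The point holds as a modest, worthwhile improvement to the protocol's design. Both 48-month models omit a pre-randomization measurement that the protocol gives good reason to regard as prognostic and that needs no new data. At 0.25 versus 0.75 survival the omission costs about 0 to 1 point of power. If placebo survival is 40%, adjustment lifts logistic power from about 80% to 82–88% at odds ratios of 2 to 4 per SD, and by under 1 point at 1.5.

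These sizes rest on the assumed prognostic strength and on a smaller effect than planned. A smaller effect is plausible. The 25% placebo figure comes from patients who had not responded to standard of care, whereas this placebo arm consists of responders to 13 weeks of open-label C1-INH. The 75% figure for C1-INH is an expectation for successful treatment, with no data cited.

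A reader might also infer that the study's reported results are affected. They are not. The study stopped with 13 subjects randomized, and the final SAP performs no formal testing and drops both 48-month analyses (SAP Sections 3, 4.2.1.3, 5, 10.2 and 10.3).

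**What to change.** In Protocol Section 10.3.3.2, or in any reuse of the design:

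- Add End-of-TP1 eGFR (mean of Weeks 11 and 12, continuous, log scale) to the 48-month logistic model and to the Cox model, keeping the strata in the latter.
- Because the logistic odds ratio then becomes conditional on eGFR, report a model-standardized risk difference with its 95% confidence interval beside it.
- Keep the models without eGFR as prespecified sensitivity analyses.
- State that the exact-logistic fallback, if needed, is run without eGFR.

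The cost is one degree of freedom per model, a standardization step, and the loss of an identical model for the primary and key secondary endpoints. No new data are needed, and the sample size and the testing hierarchy do not change. For the terminated study no action is needed.

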10.3.3.3 CCI

CCI

10.3.4 Safety Analyses

The extent of exposure to open-label C1-INH; and to double-blind C1-INH or placebo will be summarized using descriptive statistics.

10.3.4.1 Adverse events

Adverse events will be coded using the Medical Dictionary for Regulatory Affairs (MedDRA) dictionary. The number and percentage of subjects with AEs will be reported. Frequency counts and percentages will also be presented for subjects with SAEs, AEs leading to withdrawal, AEs by severity, and AEs by relationship to investigational product. Adverse events will be presented for TP1 and TP2.

10.3.4.2 Other safety evaluations

Clinical laboratory parameters for this study will be summarized by scheduled visit using descriptive statistics or frequency counts and percentages, as appropriate. Vital signs will be summarized similarly.

10.3.5 Pharmacokinetics Analyses

Blood samples will be collected for the assessment of C1-esterase inhibitor antigen concentrations and C1-esterase inhibitor functional activity at designated timepoints. C1-esterase inhibitor functional activity will be determined by a validated assay.

The observed C1-esterase inhibitor antigen concentrations and functional activity will be summarized by time, route of administration, and treatment subgroup (placebo vs C1-INH).

The parameters AUC_{0-t} and C_{max} will be estimated, if feasible, using non-compartmental PK analyses in the subset of ~20 subjects who have more frequent, sequential PK sampling at the Day 10 Visit and the Week 11 Visit.

In addition, population PK analyses may also be conducted and reported separately.

10.3.6 CCI

[figure not shown]
CCI

10.3.7 CCI

CCI

10.3.8 Other Analyses

Health-related quality of life will be assessed using the EQ-5D-3L with country specific value sets to assess the disutility associated with AMR refractory to treatment [Dolan, 1997; Cleemput et al, 2004].

10.3.9 Interim Analysis

Two unblinded analyses of the primary endpoint are planned: one interim analysis and a final analysis. The interim analysis will occur when 50% of randomized subjects (ie, 30 subjects) have been followed for 25 weeks. The final primary efficacy endpoint analysis will take place after all randomized subjects have been followed for 25 weeks after randomization. The final analysis for the study (ie, the analysis associated with the study completion date) will take place after all randomized subjects have been followed for 48 months after enrollment.

The interim analysis of the primary endpoint will be performed for purposes of sample size re-estimation and for futility monitoring. Sample size re-estimation is addressed in [Section 10.1.3](#).

To protect the integrity of the study, results of interim efficacy of the primary endpoint will only be known to the IDMC. These results will not be made public. Full details of the futility analysis and who will have access to what data/information and when they will have access will be specified in the IDMC Charter. Although statistical stopping guidelines will be provided in the charter, a number of factors must be considered thoroughly as part of the

decision to modify or terminate the trial [[Pocock, 1993](#)]. A recommendation to modify or terminate the trial will not be based solely on statistical grounds.

11 Quality Assurance

The study may be subject to an audit by CSL, an authorized representative(s) of CSL and/or inspections by an authorized regulatory authority (eg, US Food and Drug Administration [FDA]). Regulatory authorities may request access to all study documentation, including source documents for inspection and copying, in keeping with local regulations. CSL will notify the investigator of any upcoming audit/inspection.

In the event of an audit, all pertinent study-related documentation must be made available to the auditor(s). If an audit or inspection occurs, the investigator at each study site will permit the auditor/inspector direct access to all relevant documents and allocate their time as well as the time of relevant staff to discuss the findings and any relevant issues.

12 Regulatory and Ethics Considerations

12.1 Regulatory Considerations

CSL or its agents will submit the appropriate documents to the local regulatory agencies and will await approval before study start.

This study will be conducted under an FDA Investigational New Drug Application and documented in accordance with the applicable regulatory guidelines and requirements.

The procedures set out in this study protocol are designed to ensure that CSL and the investigator abide by the principles of the current ICH GCP guideline on the conduct, evaluation and documentation of this study, as described in ICH Topic E6 (Guideline for GCP). The study will also be carried out according to all applicable international and national regulatory requirements.

12.2 Institutional Review Board/Independent Ethics Committee

The investigator must submit the protocol and informed consent forms (ICFs) for review by an authorized and properly constituted (according to local guidelines) IRB/IEC. Written approval must be received from the IRB/IEC before commencement of the study.

12.3 Subject Information and Informed Consent

Informed consent of study subjects according to the standards of GCP must be implemented in this clinical study before protocol-specified procedures are carried out. Information should be given in both oral and written form and should be deemed appropriate by the IRB/IEC. Subjects, their relatives (or if necessary, legally acceptable representatives) must be given ample opportunity to inquire about details of the study.

The subject (or if necessary, legally acceptable representatives) must be provided with a copy of the signed informed consent form.

Should there be any amendments to the protocol that would directly affect the subject's participation in the study (eg, a change in any procedure), the ICF must be amended to incorporate this modification. Subjects must be informed of the change and they must sign the amended ICF indicating that they re-consent to participate in the study.

